#### 4.5.3.3 Management of Thrombocytopenic Events

Cisplatin and AZD2281 may not be dosed until Platelet count  $\geq 100 \times 10^9/L$

Each of the following thrombocytopenic events will be managed in a sequential fashion as described in [Table 6](#).

1. CTCAE grade  $\geq 3$  thrombocytopenia (platelets  $<50 \times 10^9/L$ ) at any point in the middle of a cycle
2. Platelet count  $<100 \times 10^9/L$  on Day 1 of any cycle

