Ototoxicity has been observed in up to 31% of patients treated with a single dose of cisplatin (50 mg/m^2) and is manifested by tinnitus and/or hearing loss in the high frequency range (4000 to 8000 Hz). Decreased ability to hear normal conversational tones may occur occasionally. Ototoxicity can be more severe in children than in adults and more frequent and severe with repeated administration. Hearing loss can be unilateral or bilateral and is usually not reversible. During treatment with cisplatin, it is necessary to monitor hearing at each visit. An audiogram is recommended after a cumulative dose of 360 mg/m^2. Subsequent doses of cisplatin should not be given until an audiometric analysis indicates that auditory acuity is within normal limits.

- **Myelosuppression**

Myelosuppression occurs in 25% to 30% of patients treated with cisplatin. The nadirs in circulating platelets and leukocytes occur between days 18 and 23, with most patients recovering by day 39. Leukopenia and thrombocytopenia are more pronounced at higher doses (>50 mg/m^2). Anemia (a decrease in hemoglobin of 2 g/100 ml) occurs at approximately the same frequency and with the same timing as leukopenia and thrombocytopenia.

- **Neurotoxicity**

Cisplatin neurotoxicity is characterized by peripheral neuropathies, which are sensory in nature but can also include motor difficulties such as reduced deep-tendon reflexes and leg weakness. The symptoms usually occur after prolonged therapy (4 to 7 months). Cisplatin therapy should be discontinued when serious neuropathy develops. The neuropathy, however, may progress further even after discontinuation of treatment.

In the DF/HCC neoadjuvant trial of 4 cycles of cisplatin 75mg/m^2 q21 days in 28 women with triple negative breast cancer, only one grade 4 toxicity was observed, an elevation in SGOT. There were 7 grade 3 symptomatic toxicities: one each, fatigue, abdominal pain, GI toxicity unspecified, myalgias, skin toxicity and tinnitus. Grade 3 toxicities in laboratory tests were seen in 2 women with low white blood cells and one each hyperkalemia and elevation in SGPT.

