### 4.5.3 Management of Toxicity

#### 4.5.3.1 Management of Hematological Toxicity (cisplatin and AZD2281)

The following hematologic criteria must be met on Day 1 of each cycle to administer dosing of cisplatin and AZD2281:

- ANC  $\geq 1.5 \times 10^9/L$
- Platelet count  $\geq 100 \times 10^9/L$

If both of these criteria are not met, both cisplatin and AZD2281 should be held for up to a total of 14 days until neutrophils and platelets have recovered to meet the above criteria. If cisplatin and AZD2281 must be held for greater than 14 days and the above hematologic criteria are not met, the patient should be removed from the study. Growth factor is not to be used during cycle 1 (ie any time prior to the second dose of cisplatin). Growth factor can be administered as required after the second dose of cisplatin.

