#### 4.5.3.4 Management of Hematologic NCI-CTCAE grade 3 or 4 AZD2281 Treatment Related Adverse Events

For the management for CTCAE grade 3 or 4 hematological toxicity, refer to Sections [4.5.3.1](#), [4.5.3.2](#), [4.5.3.3](#) and [Table 6](#).

**Table 6 Management of Hematologic (including Anaemic, Thrombocytopenic or Neutropenic) Grade 3 and 4 AZD2281 Treatment Related Adverse Events Whilst the Patient is Receiving Combination Therapy**

Initial Dose Level d	1 st Event Occurrence abe - Recommended Dose Reduction	2 nd Event Occurrence abe - Recommended Dose Reduction	Dose Administration
100 mg bid	50 mg bid	No reduction allowed – withdraw patient	Continuous
200 mg bid	100 mg bid	50 mg bid	Continuous
400 c mg bid	200 mg bid	100 mg bid	Continuous
50 mg bid	No reduction allowed – withdraw patient	Not applicable	Continuous
100 mg bid days 1-10 of a 21 day cycle	100 mg bid days 1-5 of a 21 day cycle	100 mg bid days 1-3 of a 21 day cycle	Intermittent
50 mg bid days 1-5 of a 21 day cycle	50 mg bid days 1-3 of a 21 day cycle	50 mg bid days 1-3 of a 21 day cycle Reduce cisplatin to 60 mg/m 	Intermittent

**Table 6 Management of Hematologic (including Anaemic, Thrombocytopenic or Neutropenic) Grade 3 and 4 AZD2281 Treatment Related Adverse Events Whilst the Patient is Receiving Combination Therapy**

Initial Dose Level d	1 st Event Occurrence abe - Recommended Dose Reduction	2 nd Event Occurrence abe - Recommended Dose Reduction	Dose Administration
50 mg bid <5 days dosing of a 21 day cycle	50 mg bid days 1-3 of a 21 day cycle Reduce cisplatin to 60 mg/m 	No reduction allowed – withdraw patient	Intermittent
50 mg bid days 1-5 dosing of a 21 day cycle with cisplatin dosed at 60 mg/m 	50 mg bid days 1-3 of a 21 day cycle Cisplatin dose to remain at 60 mg/m 	50 mg bid days 1-3 of a 21 day cycle Reduce cisplatin to 50 mg/m 	Intermittent
Dose schedule advised by safety monitoring committee	Patients on other dose schedules should have their dose decreased as appropriate in line with the above guidance		

a Hold any remaining doses of AZD2281 in the current cycle  
b Neutropenic events: Filgrastim or PEG-filgrastim may be implemented at the investigators discretion  
c If 400 mg bid dose is explored  

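### A Day 1 platelet count of 50-99 x10^9/L is hold-until-recovery in section 4.5.3.1 but a Table 6 event in section 4.5.3.3; for 50 mg bid continuous the two outcomes exclude each other

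*Protocol*

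**What the plan says.** Four parts of section 4.5.3 bear on the same patient.

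- Section 4.5.3.1 requires ANC of at least 1.5 and platelets of at least 100 x10^9/L on Day 1 of each cycle. Otherwise both drugs "should be held for up to a total of 14 days until neutrophils and platelets have recovered to meet the above criteria". Its only removal rule is that if the drugs "must be held for greater than 14 days and the above hematologic criteria are not met, the patient should be removed from the study". It gives no resumption dose.
- Section 4.5.3.3 repeats that neither drug may be given until platelets reach 100, and then states: "Each of the following thrombocytopenic events will be managed in a sequential fashion as described in" Table 6. The list has two items: Grade 3 or worse thrombocytopenia, stated as below 50, in mid-cycle; and a count below 100 "on Day 1 of any cycle".
- Table 6, in section 4.5.3.4, is titled "Management of Hematologic (including Anaemic, Thrombocytopenic or Neutropenic) Grade 3 and 4 AZD2281 Treatment Related Adverse Events Whilst the Patient is Receiving Combination Therapy". For 50 mg bid continuous it allows no reduction and directs withdrawal at the first event. Its footnote a reads "Hold any remaining doses of AZD2281 in the current cycle". The note under the table requires withdrawal at a third Grade 3 or 4 haematologic event related to AZD2281.
- Section 4.5.3.2 sends three neutropenic events to Table 6: Day 1 ANC below 1.0, febrile neutropenia, and mid-cycle Grade 4 neutropenia lasting more than 5 days.

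No section says which rule prevails.

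**The concern.** A site with a platelet count of 75 on Day 1 has instructions that do not agree. One says hold and dose again when the count recovers. One says go to Table 6. The title of Table 6 says the table is for more severe events. For a patient on 50 mg bid continuous dosing, the first two lead to opposite results.

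The timing makes this a realistic case. In its account of cisplatin toxicity the protocol says: "The nadirs in circulating platelets and leukocytes occur between days 18 and 23, with most patients recovering by day 39". Day 1 of Cycle 2 is day 22. At stake are the dose patients receive and who is still on treatment at four cycles, which the protocol requires of six evaluable patients at the selected dose. In cohorts of 3-6, one or two patients handled differently are visible in the results.

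**Working it through.** There is no stated figure to reproduce. The check applies each rule to the same Day 1 count.

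**Platelets on Day 1 (x10^9/L)**

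| Count | Section 4.5.3.1 | Section 4.5.3.3, second item | Table 6 by its title |
|---|---|---|---|
| below 50 | hold up to 14 days, dose on recovery | Table 6 event | inside, if AZD2281-related |
| 50-99 | hold up to 14 days, dose on recovery | Table 6 event | outside (below Grade 3) |
| 100 or more | dose | no event | outside |

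The middle row is the contradiction: section 4.5.3.3 sends the count to a table whose stated scope excludes it.

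**Neutrophils on Day 1 (x10^9/L), for comparison**

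| ANC | Hold? | Table 6 event? |
|---|---|---|
| below 1.0 | yes | yes |
| 1.0-1.49 | yes | no |
| 1.5 or more | no | no |

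For neutrophils the hold threshold (1.5) and the Table 6 trigger (1.0) differ, which leaves a hold-only band. For platelets both are 100, so every Day 1 hold is also a Table 6 event.

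**Consequence by row of Table 6**

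- 50 mg bid continuous: recovery within 14 days means dosing resumes under section 4.5.3.1, but section 4.5.3.3 with Table 6 means withdrawal at the first event. Both cannot be followed. In this row the same clash exists for AZD2281-related counts below 50.
- Rows with a reduction step: hold, then resume one step down, satisfies both sections. What remains open is whether a count of 50-99 triggers the step.

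**Secondary scope mismatch.** The title of Table 6 names anaemia and Grade 3 and 4 events generally, and the closing note counts any of them. Sections 4.5.3.2 and 4.5.3.3 list narrower triggers, and none for anaemia.

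**Timing.** Cycle 2 Day 1 = 21 + 1 = day 22, inside the day 18-23 window. A 14-day hold from day 22 ends at day 22 + 14 = day 36. In the 50 mg bid continuous row the two rules differ only for patients who recover by then; later recovery means removal under either.

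**Size, as illustration only.** The protocol gives myelosuppression in 25% to 30% of cisplatin patients, but no rate of Day 1 counts of 50-99.

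- Let p be an assumed chance per patient of at least one such count. The chance that a cohort of n contains an affected patient is 1 - (1 - p)^n. For p from 5% to 30% this is 14% to 66% at n = 3 and 26% to 88% at n = 6.
- Let q be an assumed chance per cycle of a recoverable count of 50-99, independent across the Day 1 checks of Cycles 2, 3 and 4. Under the withdrawal reading, the share of 50 mg bid continuous patients withdrawn by the third check is 1 - (1 - q)^3: 27%, 49% and 66% at q = 10%, 20% and 30%. The expected number needed for six completers is 6/(1 - q)^3 = 8.2, 11.7 and 17.5, or 9, 12 and 18 whole patients. Under the hold reading none of these patients is withdrawn for such counts.

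**The case against.** The strongest reply is that most of this can be read as one scheme. Section 4.5.3.1 says when dosing may resume, Table 6 says at what level, and section 4.5.3.4 tells the site to use them together. That stands for every row with a first reduction step. It does not help in the 50 mg bid continuous row, where there is no level to resume at, and it does not explain why a table titled for Grade 3 and 4 receives a count below Grade 3.

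Two stronger readings are tempting and not supported.

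- A reader might infer that footnote a, applied to a Day 1 event, suspends AZD2281 for a whole new cycle and so contradicts the 14-day hold. But section 4.5.3.2 runs Cycle 1 to the second cisplatin dose, and the synopsis ties the start of AZD2281 dosing to the cisplatin day. If cisplatin is delayed, the current cycle can be the previous one. The footnote needs a definition; it is not a proven conflict.
- A reader might infer that a 3-day Grade 4 neutropenia on 50 mg bid continuous means withdrawal. That treats a table title as a trigger. Section 4.5.3.2 gives the list, the event is not on it, and section 4.5.3.4 refers back to that section. Only the looser scope mismatch remains.

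It is also fair that the nadir passage gives timing, not depth. It shows that the conflict could arise at day 22, not how often it will.

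**Conclusion.** The point holds in a limited form. For a Day 1 platelet count of 50-99 the protocol gives inconsistent instructions, and in one planned cohort of 3-6 patients they are mutually exclusive at the first occurrence. This rests on the text alone. Every percentage and patient number above rests on an assumed rate; the per-cycle figures also assume independence across cycles, and the completer numbers matter only if 50 mg bid continuous is the dose expanded.

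The effect is on delivered dose and on who completes four cycles. A reader might infer that the primary result is compromised, but the synopsis and section 7.4.2 do not list dose-reduction or discontinuation rates among the safety variables. A reader might also infer that the DLT count changes. A platelet count of 50-99 alone is not a DLT under section 4.1.2; a treatment delay of more than 2 weeks is, and section 4.5.3.1 already provides for a hold that long. Nor does anything tie one reading to one cohort: readings would more naturally differ between sites, and all data are summarised descriptively.

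This should be fixed, but it does not invalidate the design.

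**What to change.** Reconcile sections 4.5.3.1, 4.5.3.2 and 4.5.3.3, the title and scope of Table 6, and its closing note into one list of haematological events that trigger a Table 6 step. Give one stated action for each event: hold only, hold and reduce, or withdraw. Cover Day 1 counts that are below the retreatment threshold but not as low as Grade 3, and say whether and when anaemia is a trigger. In footnote a, define which cycle is meant when Day 1 is delayed.

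Which action applies is for the sponsor and the safety monitoring committee to decide; this review takes no view. The chosen rule should apply to all cohorts.

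The cost is an amendment to one section and one table, with site re-training. It needs no added patients or procedures.

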#### 4.5.3.4 Management of Hematologic NCI-CTCAE grade 3 or 4 AZD2281 Treatment Related Adverse Events

For the management for CTCAE grade 3 or 4 hematological toxicity, refer to Sections [4.5.3.1](#), [4.5.3.2](#), [4.5.3.3](#) and [Table 6](#).

**Table 6 Management of Hematologic (including Anaemic, Thrombocytopenic or Neutropenic) Grade 3 and 4 AZD2281 Treatment Related Adverse Events Whilst the Patient is Receiving Combination Therapy**

Initial Dose Level d	1 st Event Occurrence abe - Recommended Dose Reduction	2 nd Event Occurrence abe - Recommended Dose Reduction	Dose Administration
100 mg bid	50 mg bid	No reduction allowed – withdraw patient	Continuous
200 mg bid	100 mg bid	50 mg bid	Continuous
400 c mg bid	200 mg bid	100 mg bid	Continuous
50 mg bid	No reduction allowed – withdraw patient	Not applicable	Continuous
100 mg bid days 1-10 of a 21 day cycle	100 mg bid days 1-5 of a 21 day cycle	100 mg bid days 1-3 of a 21 day cycle	Intermittent
50 mg bid days 1-5 of a 21 day cycle	50 mg bid days 1-3 of a 21 day cycle	50 mg bid days 1-3 of a 21 day cycle Reduce cisplatin to 60 mg/m 	Intermittent

**Table 6 Management of Hematologic (including Anaemic, Thrombocytopenic or Neutropenic) Grade 3 and 4 AZD2281 Treatment Related Adverse Events Whilst the Patient is Receiving Combination Therapy**

Initial Dose Level d	1 st Event Occurrence abe - Recommended Dose Reduction	2 nd Event Occurrence abe - Recommended Dose Reduction	Dose Administration
50 mg bid <5 days dosing of a 21 day cycle	50 mg bid days 1-3 of a 21 day cycle Reduce cisplatin to 60 mg/m 	No reduction allowed – withdraw patient	Intermittent
50 mg bid days 1-5 dosing of a 21 day cycle with cisplatin dosed at 60 mg/m 	50 mg bid days 1-3 of a 21 day cycle Cisplatin dose to remain at 60 mg/m 	50 mg bid days 1-3 of a 21 day cycle Reduce cisplatin to 50 mg/m 	Intermittent
Dose schedule advised by safety monitoring committee	Patients on other dose schedules should have their dose decreased as appropriate in line with the above guidance		

a Hold any remaining doses of AZD2281 in the current cycle  
b Neutropenic events: Filgrastim or PEG-filgrastim may be implemented at the investigators discretion  
c If 400 mg bid dose is explored  
d Initial dose level includes cisplatin dosed at 75mg/m^2 unless stated otherwise  
e At the investigators discretion, growth factor can be administered as required after the second dose of cisplatin

**Note:** The patient must be withdrawn if there is a third occurrence of any haematologic Grade 3 or 4 AZD2281 Treatment Related Adverse Events.

#### 4.5.3.5 Management of non-hematological toxicity attributable to AZD2281

Grade 3-4 Non-hematological toxicities observed during the course of the study and attributable to AZD2281 will first be managed by interruption of the dose. Repeat dose interruptions are to be allowed as required. The maximum duration of any dose interruption is 28 days. If an interruption of longer than 28 days is required, the patient should be withdrawn. When AZD2281 is interrupted, the patient must either recover completely or the toxicity must revert to NCI CTCAE ≤ grade 1 or to the baseline CTCAE grade before restarting treatment.

Where toxicity recurs following re-challenge with AZD2281, and where further dose interruptions are considered inadequate for management of toxicity, then the patient is to be considered for dose reduction or withdrawal.

See [Table 7](#) for instructions on dose reductions for non-hematologic CTCAE grade 3 and 4 AZD2281 treatment related adverse events whilst the patient is on combination study treatment.

Please see Section 4.5.3.6 for further information on management of grade 3-4 non-hematologic toxicities, and Section 4.5.3.7 for management of grade  $\leq 2$  non-hematologic toxicity.

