#### 4.4.6 Discontinuation of Study Treatment

##### 4.4.6.1 Criteria for Discontinuation from Study Treatment

Patients may be discontinued from investigational product (IP) in the following situations:

- Patient decision. The patient is at any time free to discontinue treatment, without prejudice to further treatment

- Adverse event
- Severe non-compliance to study protocol
- Any CTCAE grade 3 or 4 events that have not reverted to CTCAE grade 1 or less within 28-days. At the Investigator's discretion, following dose interruption, patients may be considered for dose reductions. However, if upon re-challenging with AZD2281 at the lowest reduced dose, (for guidelines refer to Section 4.5.3), any CTCAE grade 3 or 4 adverse events recur, the patient must be discontinued.
- Bone marrow findings consistent with myelodysplastic syndrome/acute myeloid leukaemia
- Disease progression

Note: Patients may continue to receive study treatment following objective progression provided that, in the opinion of the Investigator, the patient is benefiting from the treatment and does not meet any other discontinuation criteria.

In the event that cisplatin is permanently discontinued on the basis of cisplatin related toxicity, treatment with AZD2281 alone may continue. If the patient does continue on AZD2281 alone, at the discretion of the PI and in consultation with AstraZeneca Study Team Physician, the patient may be dose escalated to receive the optimal monotherapy dose (i.e.: 400 mg bid).

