#### 4.5.3.6 Management of Non-Hematologic NCI-CTCAE grade 3 or 4 AZD2281 Treatment Related Adverse Events

Treatment with AZD2281 must be interrupted for any non-hematologic CTCAE grade 3 or 4 adverse event which the Investigator considers to be related to administration of AZD2281. Repeated dose interruptions of up to a maximum of 28 days are allowed. Patients whose NCI CTCAE grade 3 or 4 event does not resolve to  $\leq$  grade 1 or to the baseline CTCAE grade after a full 28 day dose interruption should be withdrawn from the study.

Upon appropriate resolution of the toxicity (i.e., to NCI CTCAE grade 1 or to baseline CTCAE grade), the patient should restart treatment with AZD2281 but with a 50% dose reduction (as per [Table 7](#)). The dose of AZD2281 should not be reduced to less than 50 mg bid daily for patients receiving continuous AZD2281 dosing or to less than 50 mg bd for days 1-3 of a 21 day cycle for patients receiving intermittent AZD2281 dosing.

If the event recurs with the same severity, treatment should be interrupted again and, on resolution, a further dose reduction made where allowed.

Once a chemotherapy combination dose is reduced due to toxicity, combined chemotherapy dose re-escalation is not permitted.

**Table 7 Management of Non-Hematologica Grade 3 and 4 AZD2281 Treatment Related Adverse Events whilst the patient is receiving combination therapy**

Initial Dose Level c	1 st Event Occurrence - Recommended Dose Reduction	2 nd Event Occurrence – Recommended Dose Reduction	Dose Administration
100 mg bid	50 mg bid	No reduction allowed – withdraw patient	Continuous
200 mg bid	100 mg bid	50 mg bid	Continuous
400 b mg bid	200 mg bid	100 mg bid	Continuous
50 mg bid	No reduction allowed – withdraw patient	Not applicable	Continuous

**Table 7 Management of Non-Hematologica Grade 3 and 4 AZD2281 Treatment Related Adverse Events whilst the patient is receiving combination therapy**

Initial Dose Levelc	1st Event Occurrence - Recommended Dose Reduction	2nd Event Occurrence – Recommended Dose Reduction	Dose Administration
100 mg bid days 1-10 of a 21 day cycle	100 mg bid days 1-5 of a 21 day cycle	100 mg bid days 1-3 of a 21 day cycle	Intermittent
50 mg bid days 1-5 of a 21 day cycle	50 mg bid days 1-3 of a 21 day cycle	50 mg bid days 1-3 of a 21 day cycle Reduce cisplatin to 60 mg/m 	Intermittent

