50 mg bid <5 days dosing of a 21 day cycle	50 mg bid days 1-3 of a 21 day cycle Reduce cisplatin to 60 mg/m 	No reduction allowed – withdraw patient	Intermittent
50 mg bid days 1-5 dosing of a 21 day cycle with cisplatin dosed at 60 mg/m 	50 mg bid days 1-3 of a 21 day cycle Cisplatin dose to remain at 60 mg/m 	50 mg bid days 1-3 of a 21 day cycle Reduce cisplatin to 50 mg/m 	Intermittent
Dose schedule advised by safety monitoring committee	Patients on other dose schedules should have their dose decreased as appropriate in line with the above guidance		

a With the exception of grade 3 or worse neurologic toxicity, in which case both cisplatin and AZD2281 should be discontinued, as per Section 4.5.3.8

b If 400 mg bid dose is explored

c Initial dose level includes cisplatin dosed at 75mg/m^2 unless stated otherwise

**Note:** The patient must be withdrawn if there is a third occurrence of any non-haematologic Grade 3 or 4 AZD2281 Treatment Related Adverse Events.

**4.5.3.7 Management of Non-Hematologic NCI-CTCAE grade ≤2 AZD2281 Treatment Related Adverse Events whilst the patient is receiving combination therapy**

For non-hematologic toxicities of CTCAE grade ≤2 that the investigator feels are related to the administration of AZD2281, the investigators should use their discretion in deciding whether dose interruptions are necessary and should also treat the events as medically appropriate based on signs and symptoms.

Except as noted above, the dose of AZD2281 must not be modified under any other circumstances unless prior agreement is given by AstraZeneca Pharmaceuticals.

*Management of new or worsening pulmonary symptoms:* If new or worsening pulmonary symptoms (e.g. dyspnoea) or radiological abnormality occurs, an interruption in AZD2281 dosing is recommended and a diagnostic workup (including a high resolution CT scan) should be performed, to exclude pneumonitis. Following investigation, if no evidence of abnormality is observed on CT imaging and symptoms resolve, then AZD2281 treatment can be restarted, if deemed appropriate by the investigator. If significant pulmonary abnormalities are identified, these need to be discussed with the AstraZeneca Study Physician.

All dose reductions and/or interruptions (including any missed doses), and the reasons for the reductions and/or interruptions are to be recorded in the CRF.

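### The recurrence sentence in Section 4.5.3.5 does not match the first-event dose rule in Section 4.5.3.6 and Tables 7 and 8, and no precedence is stated

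*Protocol*

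**What the plan says.** Four places in the Protocol deal with AZD2281-related non-haematological Grade 3-4 toxicity on combination therapy.

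- **Section 4.5.3.5.** The dose is first interrupted, and treatment may resume only after recovery to grade 1 or less or to baseline grade. A time limit applies: "If an interruption of longer than 28 days is required, the patient should be withdrawn". No restart dose is given. Next comes the recurrence condition, "Where toxicity recurs following re-challenge with AZD2281, and where further dose interruptions are considered inadequate for management of toxicity", and its consequence, "then the patient is to be considered for dose reduction or withdrawal". The section then refers the reader to Table 7 for dose reductions and to Section 4.5.3.6 for more detail.
- **Section 4.5.3.6.** Interruption is mandatory. On resolution, "the patient should restart treatment with AZD2281 but with a 50% dose reduction", by reference to Table 7. For recurrence: "If the event recurs with the same severity, treatment should be interrupted again and, on resolution, a further dose reduction made where allowed".
- **Table 7.** It has separate columns for a first and a second event. In the 50 mg bid continuous row the first-event entry is "No reduction allowed – withdraw patient". For schedules advised by the safety monitoring committee: "Patients on other dose schedules should have their dose decreased as appropriate in line with the above guidance". Grade 3 or worse neurologic toxicity is excepted (both drugs stop), and a third occurrence means withdrawal.
- **Table 8.** For other clinically significant toxicities of grade 3 or more, AZD2281 is held for up to 28 days and then reduced according to Table 7. Toxicity that returns after resumption is dealt with as a later step.

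**The concern.** Section 4.5.3.5 attaches reduction or withdrawal to recurrence, and even then only as something to consider. Section 4.5.3.6 and the tables attach reduction, or withdrawal at the lowest continuous dose, to the first event. A site that stops at the recurrence sentence could restart a patient at the same dose after a first severe event, while another site follows Table 7.

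What is at stake is re-exposure after severe toxicity in a Phase I study whose primary objective is safety and tolerability. There is a smaller consequence for reporting. Section 7.4.3 groups the safety summaries by the initial dose received, so patients handled differently after the same first event would be summarised together.

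**Working it through.** The plan gives no figure on this point and no calculation applies. The check sets the instructions side by side for one patient: first AZD2281-related, non-neurologic, non-haematological Grade 3-4 event on combination therapy, resolved within 28 days.

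**Step 1: do the sections cover the same events?** Yes. Section 4.5.3.5 opens with Grade 3-4 toxicity attributable to AZD2281 and sends grade 2 and below to Section 4.5.3.7. Its recurrence sentence therefore falls on the events that Section 4.5.3.6 governs.

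**Step 2: what does each say at each stage?**

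| Stage | Section 4.5.3.5 | Section 4.5.3.6 with Tables 7 and 8 |
|---|---|---|
| First event | Interrupt | Interrupt |
| Not recovered after 28 days | Withdraw | Withdraw (4.5.3.6) |
| Restart after first event | No dose stated | Table 7 first-event dose, or withdraw |
| Recurrence | Consider reduction or withdrawal, if more interruptions would not suffice | Interrupt again (if of the same severity), then reduce further where allowed |
| Third occurrence | Not mentioned | Withdraw |

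The interruption, recovery and 28-day rules agree. The restart and recurrence rows do not.

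**Step 3: can one reading of the recurrence sentence reconcile them?**

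- *Reading A:* the sentence gives the whole sequence, so the first reduction comes only at recurrence. This contradicts Section 4.5.3.6, where recurrence brings a further reduction and the first one therefore belongs to the first event.
- *Reading B:* the sentence starts after a restart already reduced under Table 7. The first event is then consistent. The recurrence step still differs: Section 4.5.3.5 adds a condition about the adequacy of interruption and makes the action something to consider, while Section 4.5.3.6 calls for a further reduction where one is allowed.

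The texts differ under either reading. Only Reading A leaves the first restart open.

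**Step 4: where does the first restart matter?** Table 7's first-event actions are:

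- 200 mg bid continuous: 100 mg bid.
- 100 mg bid continuous: 50 mg bid.
- 50 mg bid continuous: withdraw. Section 4.1.1 makes this the cohort 1 dose, with 3-6 patients in Table 2.
- 100 mg bid days 1-10: days 1-5 at the same dose.
- 50 mg bid days 1-5, with cisplatin at 75 or 60 mg/m²: days 1-3 at the same dose.
- 50 mg bid for fewer than 5 days: days 1-3, with cisplatin reduced to 60 mg/m². For the days 1-3 schedule in Table 3, only cisplatin changes.

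400 mg bid, if explored, drops to 200 mg bid. Two Table 3 schedules (50 mg bid days 2-6 and 100 mg bid days 1-5) have no named row and would have to rely on the general instruction in the last row.

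**The case against.** The strongest reply is that Section 4.5.3.5 is an overview and fills its own gap. Directly after the recurrence sentence it sends the reader to Table 7 for this class of event, and then to Section 4.5.3.6, the next heading. A site that follows those pointers finds a single answer, including at 50 mg bid continuous. Section 4.1.2 leans the same way: patients with dose-limiting toxicity after cycle 1 who are benefiting may continue at a reduced dose level.

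Much of this stands. It makes the stricter rule the probable intention. What it does not do is remove the recurrence condition or say which text prevails. Because Table 7 is cited straight after that condition, a reader can take the table as saying how far to reduce once the condition is met. The reduction columns in Table 7 are headed as recommendations and Section 4.5.3.6 says should rather than must, so the stricter rule is not firm enough to settle the matter by itself.

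A reader might go further and infer that Section 4.5.3.5 permits an unreduced restart. It does not say so. Recovery is a precondition for resuming, not an entitlement to the same dose, and no section prescribes an unreduced restart.

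A reader might also see a second conflict in Section 4.4.6.1, where, at the investigator's "discretion, following dose interruption, patients may be considered for dose reductions". That sentence sits in a discontinuation bullet about Grade 3-4 events that have not reverted within 28 days, and the bullet refers to Section 4.5.3 for guidelines. It is weak support for a point about events that do resolve in that time, and the point does not depend on it.

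**Conclusion.** The point holds as an internal inconsistency in a safety rule, confined to one sentence of Section 4.5.3.5. That sentence makes reduction or withdrawal a matter to consider after recurrence; Section 4.5.3.6 and Table 7 act at the first event and again at recurrence. The consequence is greatest at 50 mg bid continuous, where a misreading would turn withdrawal into a restart.

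The conclusion assumes a non-neurologic event on combination therapy that resolves within 28 days. Monotherapy has its own rule in Section 4.5.3.9 and is outside this point.

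Two larger claims might be inferred and are not supported. One is a multiple of excess exposure: comparing an unreduced dose with the Table 7 dose measures only how large Table 7's reductions are, and the Protocol gives no basis for how often a site would misread the text. The other is an effect on dose finding: a Cycle 1 DLT is counted when the event occurs, whatever dose the patient later restarts on, so DLT counting is unaffected.

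**What to change.** Replace the recurrence sentence in Section 4.5.3.5 with:

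> After recovery from a first Grade 3-4 event, restart at the Table 7 first-event dose, or withdraw where Table 7 says so; if the event recurs, interrupt again and follow the Table 7 second-event column; withdraw at a third occurrence.

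Keep the 28-day withdrawal rule, the neurologic exception in Table 7 footnote a, and the Table 7 row for committee-advised schedules. A line in Section 4.4.6.1 saying that the restart dose for these events follows Table 7 is optional. If the sponsor's physicians do intend an unreduced first re-challenge, Section 4.5.3.6 and Tables 7 and 8 should be amended instead, so that one rule governs either way.

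The cost of the recommended change is one sentence in the next amendment and a note to sites. The tables, data collection and sample size do not change.
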